7.0 Evaluation of Side Effects

There are no significant ocular toxicity expected from SLN biopsy in the periocular region.⁸⁻¹¹ One potential side effect of the SLN biopsy for periocular tumors is the likelihood of involvement of the preauricular (parotid) lymph nodes and the risk of damage to the facial nerve during the dissection and biopsy. In our experience so far, in over 40 patients, there have been no cases of permanent facial nerve paralysis, although 3 patients with ocular tumors have had mild, temporary marginal mandibular nerve paresis, which resolved spontaneously after three weeks. This risk will be discussed with each patient prior to sentinel node biopsy. If facial nerve weakness occurs, the patient will be promptly evaluated by the ophthalmologist for protection of the corneal surface and consideration will be given to periocular reconstructive surgery, if the paresis or palsy is not improved after several months of observation.

8.0 Number of Patients

This study will be conducted at M.D. Anderson Cancer Center only. Given the rare nature of eyelid sebaceous gland carcinoma, we estimate that accrual will be about 8-10 participants a year. Our goal is to enroll 20 patients in this study. All will be enrolled at M.D. Anderson only.

9.0 Statistical Considerations

The rate of SLN positivity and the false negative events will be reported using descriptive statistics. Given the rare nature of this cancer, a total patient number of 20 is likely the maximum number that we can feasibly accrue in a few years. The estimated rate of positivity for SLN is about 15% and the estimated rate of false negative events is 8%. Based on these assumptions, the widths of 95% binomial confidence intervals based on 20 patients would be: 5%: 0.25; 10%: 0.30; 15%: 0.35; 20%: 0.38.

10. Data Analysis

Data analysis will be done at the end of patient accrual and follow up.

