2.0 Background

Sebaceous gland carcinoma of the eyelid is a rare cancer with a tendency for regional nodal metastasis. Clinically obvious regional nodal metastasis is detected in 10-20% of patients with sebaceous gland carcinoma of the eyelid according to most series.

Sentinel lymph node mapping and selective lymphadenectomy is a technique that has been successful in identifying patients with cutaneous melanoma who have microscopic regional lymph node metastasis. An early therapeutic lymph node dissection is subsequently performed in patients proven to harbor occult metastatic disease. This technique is well characterized for cutaneous melanomas in most locations. Our group has adapted SLN biopsy technique for conjunctival melanoma and eyelid sebaceous gland carcinoma.^{5,8-11,13} The potential survival benefit for patients with nodal metastasis treated with neck dissection followed by radiotherapy or systemic adjuvant therapy provides an important impetus for accurate assessment of nodal status in patients with eyelid sebaceous gland carcinoma.

The primary objective of this study is to identify the rate of SLN positivity in patients with eyelid sebaceous gland carcinoma and to determine the false negative events for the same. The SLN positivity rate refers to the number of patients who had a positive SLN on biopsy divided by the total number of patients. The false negative events refer to recurrence in a lymphatic basin that was previously deemed to harbor a "negative" SLN within the first 3 years of follow-up.

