6.0 Evaluation During Study

An ophthalmologic exam to check for recurrence of the eyelid tumor is undertaken every three months (+/- 6 weeks) during the first year and every 6 months (+/- 6 weeks) during years 2-5. A CXR will be performed 1 year (+/- 6 weeks) after removal of the primary tumor. A head and neck CT or MRI or a SPECT /CT scan is done once every 6 months (+/- 6 weeks) during the first year and then once a year (+/- 6 weeks), thereafter and as needed. An ultrasound of regional nodes will be repeated 1 year (+/- 6 weeks) after removal of primary tumor.

A study participant's inability to comply with study policies and procedures, including the inability to comply with recommended follow up visits and testing, will be withdrawn from the study by the study PI.

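### The false-negative objective is a 3-year outcome planned as a plain binomial rate, with no stated denominator and no rule for SLN-negative patients observed for less than 3 years

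*Combined protocol and SAP*

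**What the plan says.** Section 1.0 makes both the SLN positivity rate and the false negative events primary. Section 2.0 gives positivity a denominator, all patients. It defines a false negative as recurrence in a basin previously judged negative, "within the first 3 years of follow-up", and gives that quantity no denominator.

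Section 9.0 covers both objectives in one sentence: "The rate of SLN positivity and the false negative events will be reported using descriptive statistics". It assumes about 15% positivity and 8% false negative events, so objective (b) is meant as a rate and not only as a list of cases. Its sole statement on precision is that "the widths of 95% binomial confidence intervals based on 20 patients would be: 5%: 0.25; 10%: 0.30; 15%: 0.35; 20%: 0.38".

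Section 6.0 schedules eye examinations "every 6 months (+/- 6 weeks) during years 2-5" after the first year. It also has the investigator withdraw participants who cannot keep up with visits and tests. Section 10 places the analysis after accrual and follow-up are finished.

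No section gives a censoring rule, an evaluability rule or a treatment of death for objective (b).

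**The concern.** Objective (a) is settled by the pathology of the biopsy, so a binomial proportion suits it. Objective (b) is not settled then. A negative node is shown to be wrong only if nodal recurrence appears within 3 years, and it is confirmed only by observing the patient for that long. A patient last seen at 8 months has contributed some information, but neither an event nor a full 3-year non-event.

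A simple proportion forces a choice for that patient: keep as a non-event, or drop. Each choice is biased under loss to follow-up, in opposite directions, and the plan does not choose. The same data could therefore yield different primary results, with the choice made after the outcomes are known. With only one or two events expected, a few early exits can visibly change both the rate and the limit quoted for it.

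**Working it through.** **1. The plan's own figures.** Exact (Clopper-Pearson) 95% intervals for n = 20:

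| Events | Rate | Interval | Width | Plan |
|---|---|---|---|---|
| 1 | 5% | 0.001 to 0.249 | 0.247 | 0.25 |
| 2 | 10% | 0.012 to 0.317 | 0.305 | 0.30 |
| 3 | 15% | 0.032 to 0.379 | 0.347 | 0.35 |
| 4 | 20% | 0.057 to 0.437 | 0.379 | 0.38 |

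All four reproduce. The planning basis is a fixed-denominator binomial proportion on 20 patients, and no stated figure is wrong.

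**2. Patients who can have a false negative.** 20 × (1 − 0.15) = 17. Applying the 8% to them gives 17 × 0.08 = 1.36 expected events. One event gives an exact interval of 0.1% to 28.7% on 17 patients (width 0.285), against a width of 0.247 on 20.

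**3. Effect of early loss.** Inputs: true 3-year risk 8% (Section 9.0), and loss of 10, 20 or 30% by 3 years. The loss rates are assumptions; the documents give none. Take constant recurrence and loss hazards, with loss independent of recurrence. Over the 3-year window, let L = −ln(0.92) = 0.0834 and M = −ln(1 − loss).

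- Kept as non-events: K = L/(L + M) × [1 − exp(−(L + M))]
- Excluded: E = K / [K + exp(−(L + M))]

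| Loss | M | exp(−(L + M)) | Kept (K) | Excluded (E) |
|---|---|---|---|---|
| 0% | 0 | 0.920 | 8.0% | 8.0% |
| 10% | 0.1054 | 0.828 | 7.6% | 8.4% |
| 20% | 0.2231 | 0.736 | 7.2% | 8.9% |
| 30% | 0.3567 | 0.644 | 6.7% | 9.5% |

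If every loss came immediately after surgery, keeping those patients would give 0.08 × (1 − loss) = 7.2, 6.4 and 5.6%. In simulation (100,000 trials of 17 patients, same hazards, no deaths) the time-to-event estimate averaged 8.0% at all three loss rates.

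**4. One trial.** Suppose 17 SLN-negative patients, of whom 4 leave before the single recurrence and the rest are followed for 3 years.

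- Crude: 1/17 = 5.9%.
- If the 4 were lost and are censored: 1/13 = 7.7%.
- If the 4 died without nodal recurrence and death is a competing event: (13/17) × (1/13) = 1/17 = 5.9%.

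So the reason for leaving matters, not only the fact of it.

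**5. No events.** The exact upper 95% limit is 1 − 0.025^(1/n): 19.5% for n = 17 and 24.7% for n = 13. No event occurred in about 26 to 30% of the simulated trials, so this case needs a rule.

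**The case against.** A reader might infer that the plan counts early exits as proven true negatives, so that the rate is biased low and flatters the biopsy. The documents do not support that. Section 9.0 promises only descriptive statistics, its interval widths illustrate precision at the planning stage, and the withdrawal rule in Section 6.0 could equally lead to exclusion, which biases the rate upward. The direction is open.

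Death is a separate matter. Retaining as a non-event a patient who died without nodal recurrence does not bias the 3-year cumulative incidence. It is low only against a hypothetical target in which death is removed. A Kaplan-Meier analysis that censors deaths adopts that target and exceeds the actual cumulative incidence.

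Two further points stand. Examinations run to year 5 and the analysis waits for follow-up, so no administrative censoring before 3 years is planned; only loss, withdrawal or death matters. And removing the bias costs variance: in the simulation the root-mean-square error of the time-to-event estimate was 6.7, 7.0 and 7.3 percentage points at 10, 20 and 30% loss, against 6.4, 6.3 and 6.2 for the crude proportion. Excluding early exits did worst, at 7.1, 7.8 and 8.7.

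It may also be said that, with about one event, each patient's follow-up can simply be listed. That would help, but the plan does not promise it, and a listing does not define the rate.

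**Conclusion.** The point holds as an unspecified analysis of a primary objective. A 3-year outcome is planned as a fixed-number binomial rate, its precision is based on 20 patients when about 17 can have the event, and the handling of incomplete follow-up is left open.

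On 8%, the shift is about −0.4 to −1.3 percentage points if early exits are kept, and +0.4 to +1.5 if they are dropped, for 10 to 30% loss. This rests on the assumed loss rates, constant hazards and loss unrelated to recurrence. It is modest beside the interval width and vanishes if nobody leaves early. The more visible effect is on the limit quoted when no event is seen: 19.5% or 24.7% in the example, depending on who is counted. The change should be made, but the study's validity does not hang on it.

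**What to change.** In Section 9.0:

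- Keep the binomial summary for objective (a).
- For objective (b), take SLN-negative patients as the denominator. Report the 3-year cumulative incidence of nodal-basin recurrence from the SLN biopsy date, with its 95% interval. Censor loss or withdrawal at the last nodal assessment and treat death without nodal recurrence as a competing event. Give Kaplan-Meier with deaths censored only as a labelled sensitivity analysis.
- Print beside it the raw count, the number of SLN-negative patients, and the number followed to an event or for a full 3 years.
- If no event occurs, give the exact upper limit on all SLN-negative patients and, labelled as conservative, on the number fully verified. The second discards partial follow-up, so it should not stand alone.
- State precision for objective (b) on the expected SLN-negative number, about 17.

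The cost is one paragraph and a few lines of code, with no extra patients or visits. The downside is slightly larger variance and a wider interval when patients leave early. If no one is lost or withdrawn before 3 years, the point estimate equals the crude proportion among SLN-negative patients.
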